Feasibility of Home-based Virtual Reality Rehabilitation for the Upper Extremity in
Subacute and Chronic Stroke

Study Protocol

NCT03559829

September 23, 2016

The Feasibility of Home-Based Virtual Reality Rehabilitation for the Upper Extremity in Subacute and Chronic Stroke Study seeks to explore the safety, usability, and efficacy of a home based virtual reality biofeedback system to promote distal upper extremity (wrist and hand) recovery after stroke. The purpose of the study is to assess the feasibility of using a home-based virtual reality system to increase the dose of upper extremity rehabilitation in subacute and chronic stroke patients.

BACKGROUND

Stroke

Every year over 700,000 people in the US suffer at stroke. Upper extremity impairment is very common after stroke, and 15-30% of stroke survivors experience ongoing weakness in the affected arm (Van der Lee et al., 1999). The most common motor disorder which occurs after stroke is paresis, which is the inability to voluntarily activate motor neurons (Sathian et al., 2011).

Distal upper extremity strength is required to complete a number of activities of daily living (ADLs), including feeding, grooming, dressing, writing, and typing. The ability to perform such ADLs is strongly tied to quality of life (QOL) in stroke survivors (Wolf et al., 2006). However, even after intensive rehabilitation of the upper extremity, only 5-20% of patients achieve complete functional recovery (Nakayama et al., 1994).

Recent interventions for upper extremity rehabilitation in stroke including constraint induced movement therapy (CIMT) and robotic therapy. Constraint induced movement therapy involves immobilization of the non-paretic arm for 90% of waking hours and high-repetition task oriented training for at least six hours per day. Despite early studies showing some promise for motor recovery, a recent meta-analysis of 38 articles concluded that the evidence for the superiority of CIMT in comparison with other rehabilitative interventions is weak (Etoom et al., 2016).

Robot assisted arm training involves either passive movement of the affected upper extremity, or partial assistance through a movement pattern using an electromechanical device. Many of the robotic devices can also adapt as a patient recovers strength by providing less assistance or more complicated movements. While there are a number of such robots on the market, the results of studies examining facilitation of motor recovery have been mixed. A recent Cochrane Review concluded that robotic use may lead to improvements in strength and ability to perform ADLs, however they also cautioned that the quality of evidence was very low (Merholz et al., 2015).

In this pilot study, we propose to test a virtual reality home-based intervention as an alternative or supplement to traditional rehabilitation for upper extremity weakness after stroke. We are hoping to discover that the device is easily adopted by patients and increases the dose of rehabilitation, as well as potentially leads to motor recovery.

With the increasing affordability and accessibility of virtual reality (VR) systems, VR has emerged as a new platform for stroke rehabilitation. VR therapy involves using computer-based programs to simulate daily tasks and events. VR has shown promise in both allowing patients to practice activities that directly translate to their ADLs, as well as motivating them by providing a novel and interesting virtual environment. A recent Cochrane Review of VR based rehabilitation interventions concluded that it may be beneficial in improving upper limb function and ADL function, though it is unknown if these gains are sustained in the long term (Laver et al., 2015).

The RAPAEEL Smart Glove is a biofeedback device designed for distal upper extremity rehabilitation in stroke survivors. It consists of a glove-shaped sensor device and a software application which can be used with either a large screen or a portable tablet. There are multiple ADL based training games, and the system tracks the motion and posture of the wearer's distal limb as they participate. Games can be selected to focus on certain movements, such as forearm pronation/supination, wrist flexion/extension, finger flexion/extension, etc based on the needs of the wearer.

A recent single-blinded, randomized controlled trial of 46 stroke survivors compared the Smart Glove combined with standard occupational therapy (OT) to dose matched conventional upper extremity OT. The primary outcome was change in the Fugl-Meyer (FM) assessment, with secondary outcomes including fine motor tasks and quality of life (QOL) measurements. The study found greater improvements in motor impairment and QOL in the Smart Glove group (Shin et al., 2016).

Primary Hypothesis

The Neofect Smart Glove VR system will be easily adopted for home-based use, and will increase the dose of upper extremity rehabilitation received by patients with subacute and chronic stroke.

Relevance

Regaining upper extremity function is very important for stroke survivors to increase their independence and ability to perform ADLs. The large majority of outpatient stroke rehabilitation currently takes place in a therapy clinic, however access is often limited by resource allocation, financial hardship, and transportation difficulties. The Smart Glove can provide an inexpensive and convenient means for stroke patients to continue their rehabilitation in the comfort of their own home.

Patient Population

Subacute and chronic stroke patients presenting with upper extremity weakness, as identified by Stanford physicians in clinic, will be eligible for participation in this study. Patients will be screened and selected from the population of people with strokes who are seen in the Stanford Neuroscience Clinic. Patients will be allowed to participate in any scheduled outpatient rehabilitation during the study. The doctor and/or research coordinator may introduce the

study to potential candidates in-person in the Stanford Neurology Clinic, and the research coordinator may contact potential candidates by phone after the doctor's referral.

Study Sites

The Stanford University Medical Center will be the Coordinating Center for this study. Stanford's CTRU and the Neurology Outpatient Clinic will be used for study visits and assessments.

Inclusion Criteria:

- 1) Age 18 and older
- 2) Diagnosis of stroke at least three months prior to enrollment
- 3) Unilateral upper extremity functional deficit after stroke
- 4) Presence of a score of at least 2 points on the medical research council scale for wrist flexion/extension or forearm pronation/supination
- 5) Able to provide informed consent
- 6) Caregiver who is willing to be trained in use of the Smart Glove

Exclusion Criteria:

- 1) Predisposing psychological disorders which could impede participation
- 2) Severe aphasia resulting in communication difficulties
- 3) Severe pain impeding upper extremity rehabilitation
- 4) Pre-existing neurological disorder that causes motor deficits (i.e. Parkinson's disease)

Study Procedures:

Once the participant has given informed consent and enrolled in the study, they will come to Stanford's CTRU or the Neurology outpatient clinic for a total of five visits, with one visit every two weeks.

Visit one will entail the participant and identified caregiver undergoing training on the use of the Smart Glove by the research coordinator and Neofect staff. This involves donning/doffing of the glove as well as instruction as to how to use the software program. The participant will be issued a Smart Glove and a tablet preloaded with the software. Subjects will also undergo baseline functional testing, including manual muscle testing (MMT), Fugl-Meyer assessment (FM), Jebson-Taylor hand function test (JTT), and Stroke Impact Scale (SIS). This first visit is expected to take 60-90 minutes. The participant will be expected to use the Smart Glove for 60 min per day for at least 5 days per week.

The subsequent three visits will be at two week intervals and will involve the participant bringing the device to the CTRU. The research coordinator will upload the data from the device as well as troubleshoot any device-related issues. These visits will last 15-30 minutes each.

The final visit will occur after eight weeks of Smart Glove use. In addition to downloading the data, the research coordinator will also repeat functional testing functional testing, including

manual muscle testing (MMT), Fugl-Meyer assessment (FM), Jebson-Taylor hand function test (JTT), and Stroke Impact Scale (SIS). This visit will last 45-60 minutes.

Fig 1: The RAPAE Smart Glove™ system and the task-specific games of this system

Protocol Summary:

Day 0:

- Research coordinator will review the research consent form in detail with the participant and answer any questions about the study. After consent, the participant will be enrolled in the study.

Day 1:

- Smart Glove training for patient and caregiver
- Issuance of Smart Glove and tablet with preloaded software
- Baseline testing of the affected extremity:
 - Manual muscle testing (MMT)
 - Fugl-Meyer assessment (FM)
 - Jebson-Taylor hand function test (JTT)
 - Stroke Impact Scale (SIS)

Day 14:

- Download of patient use data from tablet
- Troubleshooting

Day 28:

- Download of patient use data from tablet
- Troubleshooting

Day 42:

- Download of patient use data from tablet
- Troubleshooting

Day 56:

- Download of patient use data from tablet
- Testing of the affected extremity:
 - Manual muscle testing (MMT)

- Fugl-Meyer assessment (FM)
- Jebson-Taylor hand function test (JTT)
- Stroke Impact Scale (SIS)

Neofect Smart Glove Device Description

The Neofect Smart Glove is a commercially available, non-invasive biofeedback based system for distal upper extremity rehabilitation. The Smart Glove is very lightweight and allows for easy movement of all distal upper extremity joints. It is made of an elastomer material that is simple to maintain and clean. The Bending Sensor is a variable resistor that changes as it is bent. The sensor is a 9-axis movement and position sensor that consists of 3 acceleration channels, 3 angular rate channels, and 3 magnetic field channels that measure wrist movements. They are connected to a computer system which can accurately compute the amount of individual finger movements. The available games provide various kinds of motion tasks such as ADL-related tasks presented in an entertaining manner. The learning schedule algorithm automatically adjusts to the optimal level of difficulty to balance challenge and motivation.

Fig 2: The Smart Glove

Fig 3: Using the Smart Glove in the VR environment

Risks

??????

Benefits

The participant may experience improvement in the function of their affected upper extremity.

Withdrawal

Each subject, the sponsor or its designee, and the investigator reserve the right at any time to terminate a subject's participation in the clinical investigation.

Possible reasons for study withdrawal:

- 1) Subject voluntarily withdraws consent
- 2) Subject develops an adverse event that would not allow him or her to continue in the study

- 3) Subject has an adverse event which in the opinion of the investigator warrants withdrawal from the study. The sponsor or its designee must be notified within 2 business days
- 4) A decision is made by the subject and/or investigator that the subject should be withdrawn from the study

Alternative to Participation:

There are several alternatives to participation that each potential study candidate should discuss with their physician. The alternatives including not participating and seeking no other treatment, or not participating and seeking a standard-practice treatment which is outpatient occupational therapy. Additionally, however, candidates should understand that choosing to participate is not mutually exclusive with receiving outpatient occupational therapy.

Data Collection, Transfer, and Storage

Clinical data: We will complete a stroke log that documents all patients who are treated with the Smart Glove. For patients who are considered but not enrolled in this trial, the reason for exclusion will be recorded. The data collection process will entail site staff completing case report forms (CRFs) for the initial capture of research data during patient encounters, and the data will be entered into a secure Stanford Redcap database. Clinical data obtained on the case report forms will include patient demographics, previous medical conditions, MMT, FM, JTT, and SIS scores.

References:

- 1) Etoom et al. Int J Rehab Res. 2016.
- 2) Laver et al., Coch Data Syst Rev. 2 (2015)
- 3) Mehrholz et al., Coch Data Syst Rev. 11 (2015)
- 4) Nakayama et al. Arch Phys Med. 75, 394-8 (1994)
- 5) Sathian et al., Neurorehab Neural Rep. 25, 21S-32S (2011)
- 6) Shin et al., J Neuroengineer and Rehab. 13 (2016)
- 7) Van der Lee et al., Stroke. 30, 2369-75 (1999)

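### The primary hypothesis claims an increase in rehabilitation dose received, but the only dose data listed are glove-use downloads, which equal the change in total dose only if other therapy stays constant

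*Protocol*

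**What the plan says.** The Primary Hypothesis has two parts: that the system will be readily adopted at home, and that it "will increase the dose of upper extremity rehabilitation received by patients with subacute and chronic stroke". The dose claim recurs. The opening statement of purpose is to "assess the feasibility of using a home-based virtual reality system to increase the dose of upper extremity rehabilitation", and the Background says "We are hoping to discover that the device is easily adopted by patients and increases the dose of rehabilitation", again naming adoption and dose as separate results.

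The plan leaves other therapy free to vary. Under Patient Population: "Patients will be allowed to participate in any scheduled outpatient rehabilitation during the study". Alternative to Participation adds that taking part does not rule out outpatient occupational therapy. The Background describes the study as testing "a virtual reality home-based intervention as an alternative or supplement to traditional rehabilitation".

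On glove use, Study Procedures states: "The participant will be expected to use the Smart Glove for 60 min per day for at least 5 days per week". The final visit follows eight weeks of use.

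The data listed are:

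- **Day 1:** training, issue of the device, and four functional measures (MMT, FM, JTT, SIS).
- **Days 14, 28 and 42:** download of use data, and troubleshooting.
- **Day 56:** download of use data, and the same four measures.
- **CRF items named under Data Collection, Transfer, and Storage:** demographics, previous medical conditions, and the four scores.

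**The concern.** An increase needs a reference level, and a dose received is naturally read as everything the patient gets, not the output of one device. The listed data supply neither a pre-study level of upper-extremity therapy nor the non-glove therapy during the eight weeks, and no comparison group stands in for them.

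The download reads the same whether glove sessions are added to usual therapy or replace part of it, and the Protocol's own description allows both. What is at stake is half of the primary hypothesis. An analysis plan, which was not available for this review, could define a dose outcome, but it could not supply therapy minutes that had not been recorded. What is asked at each visit has to be settled in the Protocol.

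**Working it through.** The Protocol gives no figure for change in dose, so there is nothing to reproduce. The check is an identity and an illustration.

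**Inputs from the Protocol (Study Procedures).** 60 minutes per day, five or more days a week, for eight weeks:

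- 60 × 5 = 300 min/week, as a minimum
- 300 × 8 = 2,400 min over the study

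**Inputs assumed.** The documents give no figures for adherence or other therapy.

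- *a* = share of the 300 min/week achieved: 1.0, 0.6 or 0.3
- *c* = change in other upper-extremity therapy from its pre-study level: −90 to +90 min/week

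**Identity.** Change in total dose = glove minutes + (other therapy during the study − other therapy before it) = 300*a* + *c*. The download gives 300*a*, so download minus true change = −*c*, whatever the level of use.

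**Change in total dose, min/week:**

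| Use | Download shows | c = −90 | c = −45 | c = 0 | c = +45 | c = +90 |
|---|---|---|---|---|---|---|
| 100% | 300 | 210 | 255 | 300 | 345 | 390 |
| 60% | 180 | 90 | 135 | 180 | 225 | 270 |
| 30% | 90 | 0 | 45 | 90 | 135 | 180 |

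**Over eight weeks (× 8):**

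| Use | Download shows, min | Change in total dose, min |
|---|---|---|
| 100% | 2,400 | 1,680 to 3,120 |
| 60% | 1,440 | 720 to 2,160 |
| 30% | 720 | 0 to 1,440 |

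**Size of the error.** Up to 90 min/week, or 90 × 8 = 720 min over the study, in either direction. At *c* = 0 it is nil. A fall in other therapy makes the download overstate the change; a rise makes it understate it.

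**When the direction would be wrong.** Total dose fails to rise only if *c* ≤ −300*a*, that is, if other therapy falls by at least 300, 180 or 90 min/week at the three levels of use. Within the grid the change is positive in 14 of 15 cells and zero in one. A negative result needs a larger fall or lower use: with an assumed fall of 180 min/week, 50% use gives 150 − 180 = −30 min/week and 25% use gives 75 − 180 = −105 min/week.

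**A bound.** Other therapy cannot fall below zero, so *c* cannot be lower than minus the pre-study level. For a participant with no other therapy at baseline, the download cannot overstate the change. The baseline level that would show to whom this applies is itself not among the listed items.

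**The case against.** The strongest reply is that this is a feasibility pilot in which the glove is offered on top of usual care. No procedure withdraws other therapy, participants may keep their appointments, and the Relevance section calls the device a "convenient means for stroke patients to continue their rehabilitation in the comfort of their own home". On that reading the logged minutes are the added dose, and they suffice. The direction is also fairly safe: within the illustrated range total dose almost never fails to rise, and those with little or no clinic therapy have little to lose. Finally, the CRF list is worded as open and the forms are not shown, so other therapy may be recorded on a form not seen here.

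Much of this stands. Glove minutes do serve the feasibility aim, and negligible use would count against the hypothesis. The text leans in places towards supplementing, the range is illustrative rather than evidence of a likely error, and the most that can be said of the CRFs is that no named item covers other therapy.

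Three things remain. The supplement reading still needs other therapy to be constant, and no listed item checks that. If dose means glove minutes alone, any use above zero is an increase and the claim is true almost automatically; the hypothesis should then state that meaning. And if a form not shown does capture other therapy, naming the item in the Protocol closes the gap.

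**Conclusion.** The concern holds for the visits and CRF items that the Protocol lists. They allow adoption to be described, but they do not allow an increase in total dose received to be separated from changes in other therapy in either direction.

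The download differs from the true change by exactly the change in other therapy. That is up to 90 min/week under the assumed range, set against an expected minimum of 300, and nothing if other therapy is constant. The size rests wholly on assumed adherence and therapy changes; the identity does not.

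This should be fixed. It affects half of the primary hypothesis and cannot be reliably repaired after the visits have taken place. The adoption data are unaffected.

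**What to change.** Either of two changes would do; neither alters treatment.

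**Option A: collect the missing quantity.** Add one CRF item for weekly minutes of non-glove upper-extremity therapy. Ask it at Day 1 for the preceding two weeks, and at Days 14, 28, 42 and 56 for the interval since the last visit. Report glove minutes against the stated expectation, other-therapy minutes, and their total, separately and descriptively. Change in the total should not be the sole dose outcome, and change in usual therapy should not be attributed to the glove.

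*Cost:* one question at five visits already scheduled, taking a few minutes each; for the three middle visits the Protocol says "These visits will last 15-30 minutes each". Self-reported minutes carry recall error and would sit beside device-logged ones. With no control group, drift in usual therapy still cannot be told apart from an effect of the glove.

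**Option B: restate the hypothesis, with no new data.** Word the dose half as glove minutes per week achieved against the expectation already in Study Procedures, and claim no increase in total rehabilitation dose.

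*Cost:* one sentence. The study then no longer addresses whether total dose rises.

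### Does the lack of a final download at withdrawal leave a hole in the home-use data that the protocol must close?

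*Protocol*

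**What the plan says.** The Primary Hypothesis is that the system "will be easily adopted for home-based use, and will increase the dose of upper extremity rehabilitation", so minutes of home use are the central quantity of this pilot.

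Study Procedures sets out how use is generated and collected. At visit one, "The participant will be issued a Smart Glove and a tablet preloaded with the software". The expectation is then stated: "The participant will be expected to use the Smart Glove for 60 min per day for at least 5 days per week". The next three visits come at two-week intervals, and each "will involve the participant bringing the device to the CTRU"; there, "The research coordinator will upload the data from the device as well as troubleshoot any device-related issues". The final visit, after eight weeks, includes another download. The Protocol Summary repeats the item "Download of patient use data from tablet" at Days 14, 28, 42 and 56.

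Under Withdrawal, the subject, the sponsor and the investigator "reserve the right at any time to terminate" participation. Four reasons follow, one with a deadline for notifying the sponsor. The section does not mention an exit visit, a last download or the return of glove and tablet.

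Data Collection, Transfer, and Storage calls for a log of everyone treated with the glove. It says the case report forms will include demographics, medical history and the four test scores; use data are not in that list.

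**The concern.** Read literally, the use log reaches the study only when the participant comes to a visit with the device. Someone who leaves between visits takes the unread part of the log home. No remote transfer, home collection or mailed return is described, and no second record of use is listed.

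The gap falls only on leavers, who tell the most about ease of adoption. Their last days show whether they had already put the glove aside or were still using it when they left for another reason. Those two histories mean different things for feasibility, and without the log they look alike. An analysis plan can say how to treat a missing interval, but it cannot recover a log that was never read. It therefore seemed reasonable to ask the protocol for a retrieval step.

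**Working it through.** **Inputs from the protocol.** Expected use is 60 min per day on at least 5 days per week, for 8 weeks. Downloads are on Days 14, 28, 42 and 56. Sample size, dropout rate, adoption threshold and a rule for unread intervals are not stated, so there is no figure of the plan's own to reproduce.

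**Loss for one leaver whose tablet is not recovered**

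- Minimum rate: 60 × 5 = 300 min/week; 300 × 8 = 2400 min in total; one two-week interval is 300 × 2 = 600 min; 600/2400 = 25%.
- Use on all 7 days: 60 × 7 = 420 min/week; 420 × 8 = 3360 min; one interval is 840 min; 840/3360 = 25%.
- One interval is the ceiling only if every earlier visit was attended. Someone who attends Day 14, misses Day 28 and leaves on Day 40 has 40 − 14 = 26 unread days. At the minimum rate that is 26 × 300/7 = 1114 min.
- Someone who attends no download visit loses everything used.
- A missed visit alone costs nothing if the participant returns later with the log still on the tablet. A participant who stops using the glove but keeps attending is recorded correctly.

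**Study level, illustration only.** Assume that a share w of 10% to 40% leaves, that everyone uses the glove at 300 min/week until leaving or Day 56, that no leaver's tablet is recovered, and that unread days are counted as zero. None of these four assumptions is in the protocol.

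True mean = (1 − w) × 2400 + w × (use up to leaving). Understatement = w × (unread use).

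| All leavers leave on | Use up to leaving (min) | Unread (min) | Understatement of mean, w = 10% | w = 40% |
|---|---|---|---|---|
| Day 15 | 15 × 300/7 = 643 | 643 − 600 = 43 | 4/2224 = 0.2% | 17/1697 = 1.0% |
| Day 20 | 20 × 300/7 = 857 | 857 − 600 = 257 | 26/2246 = 1.1% | 103/1783 = 5.8% |
| Day 13 | 13 × 300/7 = 557 | 557 | 56/2216 = 2.5% | 223/1663 = 13.4% |

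The spread from 0.2% to 13.4% comes entirely from the assumed share and leaving day.

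**Direction.** The table assumes full use until leaving. The worry, however, is that leavers may already have stopped. Take a leaver who used the glove at the minimum rate to Day 14, stopped, and left on Day 20.

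- Unread use is 0, so counting unread days as zero gives no error.
- If unread days are dropped instead, the daily rate is 600/14 = 43 min, against a true 600/20 = 30 min, an overstatement.

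The same gap can therefore lower the result, raise it or leave it unchanged, depending on the leaver's behaviour and the analyst's rule. The protocol fixes neither.

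**The case for a change.** The best argument for a change is that this is a collection step, which belongs in the protocol and cannot be repaired at analysis. The protocol has a Withdrawal section that goes as far as a notification deadline, and one or two sentences there would protect the main measure at little cost. The reading of the text behind this argument is correct: no remote transfer, exit download or device return is described, and the first download is on Day 14.

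What does not stand is the step from silence to defect.

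- The protocol neither requires nor excludes recovery of the tablet. It schedules downloads at visits; it does not say that data may be read at no other time.
- Return of glove and tablet is not described for completers at Day 56 either. That suggests equipment logistics were left outside this document altogether, rather than overlooked for leavers. Consent wording, where such terms might sit, was not available to check.
- Several of the listed reasons for withdrawal involve an adverse event or a decision by the investigator, so there is contact in which the tablet can be collected. The exposed group is mainly those who are silently lost or who withdraw consent. For the latter, retrieval might not be permitted whatever the protocol said.
- Reading the log every two weeks already limits the loss compared with a single download at the end, and the log of treated patients keeps leavers in the denominator.

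**Conclusion.** No change to the plan is called for. The observation is accurate, but it concerns an operational detail that a coordinator would ordinarily settle by recovering issued equipment and reading its log. The protocol states no wrong or contradictory rule on this point.

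The most that can be said about size is per leaver, and only if the tablet is not recovered: up to 600 of 2400 minutes at the minimum expected rate when all earlier visits were attended, more when a visit was skipped, and all use when no download visit was attended. At study level neither the size nor the sign of the effect can be derived. The illustrative 0.2% to 13.4% rests on an assumed dropout share, assumed leaving days, full use until leaving, no recovery of any tablet and zero-counting of unread days. The protocol also sets no adoption threshold, so no conclusion is shown to turn on these minutes. How unread intervals are treated is properly left to the analysis plan.

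### Participants withdrawn before Day 56 have no planned post-baseline functional test, so the exploratory pre-post change rests on those who stay

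*Protocol*

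**What the plan says.** Under Study Procedures, participants attend "for a total of five visits, with one visit every two weeks". Visit one includes baseline MMT, FM, JTT and SIS. For the next three visits the content is: "The research coordinator will upload the data from the device as well as troubleshoot any device-related issues". No functional test is mentioned there. On the last visit the same section says "The final visit will occur after eight weeks of Smart Glove use", and the four instruments are repeated then.

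The Protocol Summary gives the same plan by calendar day. Days 14, 28, 42 and 56 each list "Download of patient use data from tablet". The functional tests appear on Day 1 and Day 56 only.

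The Withdrawal section allows the subject, the sponsor or the investigator to end a subject's participation, and lists four possible reasons:

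- Reason 1: consent is voluntarily withdrawn.
- Reason 2: "Subject develops an adverse event that would not allow him or her to continue in the study".
- Reason 3: "Subject has an adverse event which in the opinion of the investigator warrants withdrawal from the study".
- Reason 4: "A decision is made by the subject and/or investigator that the subject should be withdrawn from the study".

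The section describes no exit visit, no functional test at exit and no option to stop the device while staying in follow-up.

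The Primary Hypothesis is that the system will be easily adopted at home and "will increase the dose of upper extremity rehabilitation received by patients". Efficacy is one of the things that the opening statement sets out to explore.

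**The concern.** Stopping a device and leaving a study are different events. A participant whose wrist becomes painful may have to stop the glove yet be willing to come back for one more test. This protocol has a path only for leaving the study, and an adverse event or an investigator's decision can lead straight onto it. Because the only post-baseline functional test is at the last visit, leaving early means having no functional outcome at all.

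The before-after change in MMT, FM, JTT and SIS is the only efficacy information that the schedule produces. If those who leave are absent from it, it describes people who tolerated the glove and stayed. Those who stopped because of an adverse event, or because they or the investigator decided they should, are informative in a study of home feasibility.

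This is a protocol matter rather than one for the SAP. An SAP can say how missing scores are handled, but it cannot create a visit or recover a measurement that was never taken.

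**Working it through.** The protocol states no figure on this point to reproduce, and gives no sample size or dropout rate. The check is a reading of the schedule against the withdrawal reasons, with one line of arithmetic on exposure.

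**Step 1. What each visit collects** (Study Procedures and Protocol Summary)

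| Visit | Use data downloaded | MMT, FM, JTT, SIS |
|---|---|---|
| Day 1 | no (glove issued) | yes, baseline |
| Day 14 | yes | no |
| Day 28 | yes | no |
| Day 42 | yes | no |
| Day 56 | yes | yes |

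Function is tested at 2 of 5 visits and at 0 of the 3 interim visits.

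**Step 2. What a participant who leaves early contributes.** The expected minimum use is 60 minutes a day on 5 days a week.

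- Per two weeks: 60 min × 5 × 2 = 600 min = 10 h.
- Over eight weeks: 10 h × 4 = 40 h.

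Assuming exactly this minimum use, withdrawal just after an interim visit gives:

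| Withdrawn just after | Hours of use | Share of 40 h | Downloads done | Post-baseline functional score |
|---|---|---|---|---|
| Day 14 | 10 | 25% | 1 of 4 | none |
| Day 28 | 20 | 50% | 2 of 4 | none |
| Day 42 | 30 | 75% | 3 of 4 | none |

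A participant can thus complete three quarters of the planned dose and still have no functional outcome. All four instruments are lost together, because they share one visit.

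**Step 3. Which withdrawals are affected.** Reason 1 is withdrawn consent, and no protocol text can or should override it. Reasons 2 and 3 are adverse events and reason 4 is a decision by the subject or investigator. In these, some participants might still agree to a final test, but the plan offers them none.

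**Step 4. What happens to someone who simply stops using the glove.** Non-use is not among the listed reasons, the visits run every two weeks, and the last is Day 56. On that schedule such a participant stays in the study and is tested. The protocol does not say so outright.

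**Step 5. Effect on the primary hypothesis.** Use data are downloaded at each of the four return visits, so most early leavers contribute some. What is lost is use since the last download and, for someone withdrawn before Day 14, any scheduled download. Adoption and dose are therefore largely, though not wholly, protected.

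**The case against.** The strongest case on the other side is that little is at stake. This is a pilot whose one stated hypothesis concerns adoption and dose. The functional change has no control group, and participants may continue any scheduled outpatient rehabilitation, so even complete data could not attribute improvement to the glove. The group that the fix can reach is narrow. Reason 1 is out of reach, a subject's own decision under reason 4 may be hard to tell from withdrawn consent, and some people with an adverse event under reason 2 could not do a motor test. All of this stands. It limits the importance of the point but does not remove the gap.

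A second objection also stands: a test done when someone stops, say at week 2, is not an eight-week change, and pooling the two would create a new problem.

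Two stronger readings are tempting and are not supported:

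- *That the final visit depends on weeks of actual use.* A reader might infer from "The final visit will occur after eight weeks of Smart Glove use" that a pause postpones the test, or that someone who stops for good never has it. But five visits at two-week intervals and a listed Day 56 fix the calendar. Eight weeks is 56 days, and no rule for pausing or extending the period exists. The phrase most naturally means elapsed time at home. Replacing it with Day 56 would only clarify the wording.
- *That the pre-post change will be biased in a known direction, or by an amount that can be calculated.* That would need the share who leave and how their change compares with that of those who stay. The protocol gives neither. Illustrative values can be chosen to give bias in either direction, so they show no harm specific to this trial.

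**Conclusion.** The point holds in a limited form. Followed as written, the plan provides no post-baseline functional score for anyone withdrawn before Day 56, including those withdrawn for an adverse event or by decision, so the exploratory pre-post change rests on those who stay. This follows from the schedule and the Withdrawal section alone and needs no assumption about dropout. The hours of exposure in the working assume use at exactly the stated minimum.

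The number of participants affected and the size and direction of any bias are unknown. Closing the gap would make an uncontrolled exploratory measure more complete; it would not make it causal. The point is worth acting on because the loss cannot be repaired afterwards and costs little to prevent. It is a cheap improvement, not a flaw that undermines the study.

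**What to change.** Add two or three sentences to the Withdrawal and Study Procedures sections:

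1. Stopping the glove for any reason, including an adverse event, is not withdrawal from the study.
2. Unless consent is withdrawn, the final download and the MMT, FM, JTT and SIS are done on calendar Day 56, whether or not the glove is still in use.
3. A participant who will not return on Day 56 is offered the tests at the time of stopping. Those scores are reported separately and not pooled with the eight-week change.

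As a wording clarification only, date the final visit by Day 56 instead of by weeks of use.

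The cost is the text change and, for each participant who stops, the already planned 45-60 minute final visit or an earlier one in its place. That is a small burden on those participants. Some will decline or be unable to do the tests, and those who withdraw consent will stay missing. No new instrument or larger sample is needed.
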